
> 60/minute (< 2 months of age)

> 50/minute (2 to < 12 months of age)

> 40/minute (12 to 24 months of age)

⁴ Confirmed RSV infection defined in Section 4.2.6.3⁵ RSV (nasal swab) sampling and testing as specified in Table 12.⁶ Hospitalization is defined as admission for observation or treatment based on the judgement of a health care provider.**4.2.6.3. RSV infection**

The sponsor will analyze nasal swabs by quantitative reverse transcription polymerase chain reaction (qRT-PCR) for the presence of RSV A/B. A positive (RSV A or B) test result constitutes a case of RSV infection. Refer to Table 11, Table 12 and Section 8.1.

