| | | - | - | RTI hospitalization | Collect a nasal swab (if possible) from any subject hospitalized with a RTI (or soon after discharge, as long as symptoms are ongoing). NOTE: Collection of a nasal swab for sponsor testing is additional to and DOES NOT REPLACE any specimen collection (per local standard of care) for testing by the local laboratory to establish a fast and accurate diagnosis for the hospitalization. In the case of hospitalization, local testing for RSV infection should be performed if feasible. If other specimens are collected and tested locally as per local standard of care, results will be recorded in the eCRF. However, only the sponsor laboratory results will be used when applying the case definitions for data analysis in Section 4.2.6 Thus, where mandated by the protocol, every effort should be made to obtain samples that can be analyzed by the sponsor (or sponsor-designated) laboratory. |

CONFIDENTIAL

209544 (RSV MAT-004)
Protocol Amendment 3 Final

Table 12 Biological samples – infant subjects

| Infant Sample type | Collected to Evaluate | Minimum Quantity per subject | Unit | Time point | Additional Information |
|--------------------|-----------------------|------------------------------|------|---|---|
| Blood | Immune response | ~2.5 | ml | Visit 1-NB (Within 3 days after birth) | ONLY if cord blood cannot be collected. Volume must be reduced if weight \leq 2.5 kg. [Trial-related blood loss for infant subjects should be \leq 1 % at each timepoint. Total blood volume is estimated at 80 to 90 ml/kg body weight, and venipuncture should not exceed ~ 1.6 ml for a 2kg baby or 2.0 ml for a 2.5 kg baby.] Refer to the Laboratory Manual for additional information. |
| | | ~2.5* | ml | Visit 2-NB (Day 43) | |
| | | ~2.5* | ml | Visit 3-NB (Month 4) | |
| | | ~2.5* | ml | Visit 4-NB (Month 6) | |
| | | ~ 2.5 ~5.0 | ml | Minimum TOTAL, assuming body weight > 2.5 kg and cord blood (Table 11) collected Minimum TOTAL, assuming body weight > 2.5 kg and cord blood NOT collected | |
| Nasal swab | Presence of RSV A / B | - | - | Assessment Visit (Infant RTI) | Collect at least one nasal swab for each RTI reported A nasal swab should be collected at the first RTI assessment visit and at the first follow-up RTI assessment visit (if criteria for follow-up are met – see Sections 8.4.4.2 and 8.4.7 If more than one follow-up assessment visit is conducted, additional nasal swabs may be collected at the Investigator's discretion. |

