| | | - | - | RTI hospitalization | Collect (if possible) from any subject hospitalized with a RTI (or soon after release, as long as symptoms are ongoing). Collection of a nasal swab for sponsor testing is additional to and DOES NOT REPLACE any specimen collection (per local standard of care) for testing by the local laboratory to establish a fast and accurate diagnosis for the hospitalisation. In the case of hospitalization, local testing for RSV infection should be performed if feasible. If other specimens are collected and tested locally as per local standard of care, results will be recorded in the eCRF. However, only the sponsor laboratory results will be used when applying the case definitions for data analysis in Section 8.4.7. Thus, where mandated by the protocol, every effort should be made to obtain samples that can be analyzed by the sponsor (or sponsor-designated) laboratory. |

*Only from infant subjects in the sample collection subcohort for the visit. Each infant is assigned to a single subcohort.

CONFIDENTIAL209544 (RSV MAT-004)
Protocol Amendment 3 Final**8.1.2. Laboratory assays**

Assays performed to evaluate immune response / the presence of RSV infection are listed below.

Table 13 Antibody determination

| System | Component | Method | Laboratory |
|--------|--|--------|---|
| SERUM | RSV-A NAb (RSV-A Neutralizing Antibody) | NEUT | GSK Biologicals** or GSK designated lab |
| SERUM | RSV-B NAb (RSV-B Neutralizing Antibody) | NEUT | GSK Biologicals** or GSK designated lab |
| SERUM | Respiratory Syncytial Virus Pref3 Ab.IgG (RSVPreF3 IgG antibody concentration) | ELISA | GSK Biologicals** or GSK designated lab |

ELISA = enzyme-linked immunosorbent assay; **NEUT** = Neutralization; ** GSK Biologicals laboratory refers to the Clinical Laboratory Sciences (CLS) facilities in Rixensart, Belgium, Marburg, Germany and Wavre, Belgium.

Table 14 Molecular Biology

| System | Component* | Method | Unit | Laboratory |
|---------------------|-----------------------------------|--------|-----------|---|
| NASMUC (Nasal swab) | Respiratory Syncytial Virus A RNA | QRTPCR | Copies/mL | GSK Biologicals or GSK designated lab** |
| NASMUC (Nasal swab) | Respiratory Syncytial Virus B RNA | QRTPCR | Copies/mL | GSK Biologicals or GSK designated lab** |

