9.3.3.1.3. Maternal and Infant subjects

- Diagnosis during the study with an immunological disorder or occurrence during the study of a condition (other than the study pregnancy) capable of altering immune response. For evaluation of immunogenicity endpoints in maternal and infant subjects, this includes RSV infection confirmed either locally or by GSK Biologicals during the specified analysis interval.
- Any investigational or non-registered product (drug or vaccine) other than the study vaccine/product administered during the specified analysis interval.

9.3.3.2. Other situations that may lead to elimination of a subject from per-protocol analyses

- Protocol violation(s) linked to the inclusion/ exclusion criteria, including age.
- Study vaccine/product not administered as specified by the protocol.
- Failure to comply with the post-vaccination immunogenicity blood sampling schedule at a given time-point ([Table 2](#), [Table 4](#)).

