9.4.4. Secondary endpoints**9.4.4.1. Safety**

| | Secondary Safety Endpoints | Statistical Analysis Methods |
|--------------------------|---|---|
| Maternal subjects | 
From Day 1 (Visit 1) through 6 months after delivery (Visit 8), occurrences of SAEs, MAEs and AEs leading to study withdrawal.
 
Occurrence of RSV-associated medically attended RTIs (RSV-MA-RTIs) up to 6 months post-delivery (Visit 8)
 | 
The number and percentage of maternal subjects with at least one SAE, AE leading to study withdrawal, MAE from Day 1 up to 6 months after delivery with exact 95% CIs will be tabulated by group and by Medical Dictionary for Regulatory Activities (MedDRA) preferred term.
 
By-subject listings of SAEs, AEs leading to study withdrawal and MAEs will be prepared (but will not be released until the final, unblinded, analysis has been completed).
 
The number and proportion of subjects with at least one RSV-associated MA- RTI (with 95 % CI) will be calculated and tabulated.
 |
| Infant subjects | 
From birth through 6 months (Visit 4-NB) after birth, occurrences of SAEs, AEs leading to study withdrawal, and medically attended AEs
 
From birth through 1 year (Visit 5-NB) after birth, occurrences of SAEs, AEs leading to study withdrawal, and MAEs
 | 
For each category:
 
 SAE, AE leading to study withdrawal, MAEs 
The number and proportion of infant subjects who experienced at least one event from birth up to 6 months after birth and the number and proportion of infant subjects who experienced at least one event from birth up to 1 year after birth will be tabulated with 95% CI by group.
 
By-subject listings of SAEs, AEs leading to study withdrawal and MAEs will be prepared.
 |
| | 
From birth to 6 months (Visit 4-NB), occurrences of RSV-associated LRTI(s), Severe LRTI(s), very severe LRTIs and RSV-associated hospitalizations (according to the case definitions in Section 4.2.6)
 | 
For each category:
 
 RSV-associated LRTI, Severe LRTI, Very severe LRTI RSV-associated hospitalization 
The number and proportion (with 95% CI) of subjects with at least one event will be calculated and tabulated by group.
 |

CONFIDENTIAL209544 (RSV MAT-004)
Protocol Amendment 3 Final**9.4.4.2. Immunogenicity**

| | Secondary Immunogenicity Endpoints | Statistical Analysis Methods |
|--------------------------|---|--|

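### RSV cases count only on a sponsor-laboratory result, so an infant hospitalised with locally confirmed RSV but no sponsor-tested swab drops out of the severe-disease counts

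*Protocol*

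**What the plan says.** **Definition.** Under Section 4.2.6.3, RSV infection rests on the sponsor's test: "The sponsor will analyze nasal swabs by quantitative reverse transcription polymerase chain reaction (qRT-PCR) for the presence of RSV A/B". No route through a local result is given. Table 8 builds RSV-LRTI, severe LRTI, very severe LRTI and RSV hospitalisation on that confirmation.

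**Restriction.** Table 12 (infants) repeats it: "However, only the sponsor laboratory results will be used when applying the case definitions for data analysis". Table 11 (mothers) says the same: "However, only the sponsor laboratory results will be used when applying the case definitions for data analysis in Section 4.2.6".

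**Sponsor swab at admission.** Table 12 does not guarantee it: "Collect (if possible) from any subject hospitalized with a RTI (or soon after release, as long as symptoms are ongoing".

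**Local test.** The same cell asks for it: "In the case of hospitalization, local testing for RSV infection should be performed if feasible". On recording: "If other specimens are collected and tested locally as per local standard of care, results will be recorded in the eCRF".

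**Analysis.** Section 9.4.4.1 summarises the infant RSV endpoints simply: "The number and proportion (with 95% CI) of subjects with at least one event will be calculated and tabulated by group".

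**Use of local results elsewhere.** For elimination from the per-protocol immunogenicity analysis, Section 9.3.3.1.3 accepts either source: "this includes RSV infection confirmed either locally or by GSK Biologicals during the specified analysis interval".

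**The concern.** The protocol collects the information that would fill a missing sponsor result and then bars its use. An infant admitted with locally proven RSV and never swabbed for the sponsor during that illness does not meet any of the RSV definitions in Table 8.

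The protocol itself foresees ways for this to happen. Care may be given by providers outside the study (Section 8.4.2). Assessment visits may be missed and completed from medical records (Section 8.4.5.3). Under pandemic measures, event-driven visits may become remote contacts, and nasal swabs may be taken only with centrally provided supplies (Section 8).

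These counts matter because they are the study's check on enhanced respiratory disease. Section 8.2.3.4 compares progression from RSV infection to severe disease or hospitalisation with a historical 80%, illustrated with 5 or 10 infected infants. At such sizes a single unclassified infant can matter, and for a harm endpoint an undercount of severe cases errs in the unsafe direction.

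**Working it through.** **Inputs (Section 8.2.3.4 and Table 20).** Historical progression rate 80%; assumed rate 10%; one-sided 5% error; at least 5 infections needed; an upper 95% limit below 80% is read as unlike the historical vaccine.

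**1. Reproduce the protocol's figures.**
- Power with 5 infections, rejecting 80% if at most 1 progresses. Error = 0.2^5 + 5(0.8)(0.2^4) = 0.0067. Power = 0.9^5 + 5(0.1)(0.9^4) = 0.9185. This agrees with the stated 90% or more.
- Table 20 upper limits are two-sided 95% Clopper-Pearson: U(x, n) = the 97.5th percentile of Beta(x+1, n-x). This gives 71.6 and 85.3 for 1/5 and 2/5, and 44.5, 55.6, 65.2, 73.8 and 81.3 for 1/10 to 5/10. All match after rounding.

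**2. Effect of one hospitalised infant without a sponsor result.** A hospitalised infant counts as a progressor, so the loss removes one from both numerator and denominator. The fall in the observed rate is x/n - (x-1)/(n-1) = (n-x)/[n(n-1)], which is positive whenever x < n.

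| All cases counted | Upper limit | One lost | Upper limit | Crosses 80%? |
|---|---|---|---|---|
| 5/10 | 81.3% | 4/9 | 78.8% | yes |
| 4/10 | 73.8% | 3/9 | 70.1% | no, already below |
| 2/5 | 85.3% | 1/4 | 80.6% | no |

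With two lost from 2/5, 0/3 has an upper limit of 70.8%, which does cross. Of the seven rows in Table 20, only 5/10 crosses on a single loss.

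**3. Effect of missed mild cases.** These leave the denominator only, so the observed rate rises. Missing two mild cases turns 4/10 (73.8%) into 4/8 (upper limit 84.3%).

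**4. Range under assumed capture rates.** The protocol gives no capture rate, so these are assumptions. Take 10 true infections. The table shows the probability that the upper limit falls below 80%.

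| Severe cases captured | Mild cases captured | True progression 50% | True progression 80% |
|---|---|---|---|
| 100% | 100% | 0.377 | 0.006 |
| 90% | 100% | 0.478 | 0.017 |
| 80% | 100% | 0.546 | 0.026 |
| 50% | 100% | 0.687 | 0.064 |
| 80% | 80% | 0.366 | 0.012 |
| 100% | 80% | 0.288 | 0.004 |

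If only severe cases are missed, a reassuring reading becomes more likely. If only mild cases are missed, it becomes less likely.

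**The case against.** **Selective loss is not shown.** A reader might infer that the sickest infants are the least likely to have a sponsor swab, so that the endpoint is biased towards reassurance. The protocol does not support this, and it gives sicker infants more opportunities. Table 12 asks for a swab at the first assessment visit and the first follow-up visit. Section 8.4.4.2 asks for a visit ideally within 24 hours for breathing difficulty or wheezing, and another on worsening. Section 8.4.6 asks for a swab on admission. A sponsor swab taken earlier in the same illness satisfies the definition, and Table 12 presses sites to obtain sponsor samples. The example of a missed visit in Section 8.4.5.3 is an illness that resolved while the family was travelling, which is a mild-case loss. This objection stands: the net direction is unknown.

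**Contradiction with Section 9.3.3.1.3.** A reader might infer that the protocol contradicts itself by accepting local confirmation there. It does not. A sensitive trigger for removing subjects from a per-protocol immunogenicity set and a specific, uniform assay for a case endpoint serve different purposes. The passage shows only that local results are regarded as informative.

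**Expected case numbers.** A reader might take 5 to 10 as the forecast number of infections. Section 8.2.3.4 says at least 5 are needed and presents Table 20 as examples. No expected count is given.

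**The event stays visible.** Respiratory hospitalisations are reported as SAEs within 24 hours (Section 8.3.1), the IDMC receives unblinded data about monthly (Section 8.2.3.3.3), Table 8 defines all-cause LRTI without RSV confirmation, and all analyses are descriptive (Section 9.1). This reduces the consequence but does not restore the infant to the RSV counts.

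**Replacing the definition would bring its own bias.** Suppose 4 of 10 infections progress and 80% of all cases are captured. The current rule then gives 3.2/8 = 40%, which is correct. Rescuing every hospitalised case, and taking all 4 progressors to be hospitalised, gives 4/(4 + 4.8) = 45.5%. This stands against changing the main definition. It does not count against a supplementary analysis.

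**Conclusion.** The point holds in a limited form. The protocol fixes sponsor-only confirmation, makes the admission swab conditional, and records local results without using them for case classification. A hospitalised infant with a local positive and no sponsor-tested swab for that illness is left out of the RSV counts and the progression rate. That exclusion follows from the definitions, although the protocol does not spell it out. Section 9.4.6.3 leaves case accountability to the SAP, which is not at hand, but the sponsor-only rule is already set in the protocol.

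For each such infant the RSV hospitalisation count falls by one and the observed progression rate falls by (n-x)/[n(n-1)]: 5.6 percentage points at 5/10, enough to move the upper limit from 81.3% to 78.8%. How often this would occur, and whether losses among severe or mild cases dominate, cannot be determined from the protocol. It is a cheap improvement to a harm endpoint and does not show that the planned result would be biased.

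**What to change.** Keep the sponsor-laboratory definition as the main analysis and add the following to the plan:

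1. A pre-specified supplementary analysis of RSV hospitalisation, the LRTI severity categories and the Table 20 progression counts. It would also count subjects with a local RSV-positive result in the eCRF when no sponsor result exists for that illness.
2. A report, by group, of the number of respiratory hospitalisations without a sponsor result.
3. The main and supplementary counts side by side.

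When Table 12 is edited, correct its cross-reference for the case definitions. It points to Section 8.4.7, which covers follow-up of illnesses, whereas Table 11 points to Section 4.2.6.

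The cost is wording and a few tables from data already in the eCRF, with no new sample or visit. The downside is that local assays vary, and local positives will come mainly from hospitalised infants, which can raise the progression rate. That is the conservative direction for a harm endpoint, and showing both counts lets the reader judge it.

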8.1.3. Immunological read-outs

Table 15 Immunological read-outs

| Blood sampling timepoint | | No. subjects | Component | Components priority rank |
|---|--|--------------|--|--------------------------|
| Type of contact and timepoint | Sampling timepoint | | | |
| Maternal subjects | | | | |
| V1 (Day 1) | pre vaccination | up to 300 | RSV-A NAb (neutralizing antibody) | 1 |
| | | | Respiratory Syncytial Virus PreF3 Ab.IgG (concentration) | 3 |
| | | | RSV-B NAb (neutralizing antibody) | 2 |
| V3 (Day 31) | post vaccination | up to 300 | RSV-A NAb (neutralizing antibody) | 1 |
| | | | Respiratory Syncytial Virus PreF3 Ab.IgG (concentration) | 3 |
| | | | RSV-B NAb (neutralizing antibody) | 2 |
| V5 (Delivery) (venous blood and cord blood)* | delivery | up to 300 | RSV-A NAb (neutralizing antibody) | 1 |
| | | | Respiratory Syncytial Virus PreF3 Ab.IgG (concentration) | 3 |
| | | | RSV-B NAb (neutralizing antibody) | 2 |
| V6 (Day 43 post-Delivery) | post delivery | up to 300 | RSV-A NAb (neutralizing antibody) | 1 |
| | | | Respiratory Syncytial Virus PreF3 Ab.IgG (concentration) | 3 |
| | | | RSV-B NAb (neutralizing antibody) | 2 |
| Infant subjects | | | | |
| V1-NB (Birth)* | birth (only if cord blood cannot be collected) | Event-driven | RSV-A NAb (neutralizing antibody) | 1 |
| | | | Respiratory Syncytial Virus PreF3 Ab.IgG (concentration) | 3 |
| | | | RSV-B NAb (neutralizing antibody) | 2 |
| V2-NB (Day 43) | post birth 1 | up to 100 | RSV-A NAb (neutralizing antibody) | 1 |
| | | | Respiratory Syncytial Virus PreF3 Ab.IgG (concentration) | 3 |
| | | | RSV-B NAb (neutralizing antibody) | 2 |
| V3-NB (Day 121) | post birth 2 | up to 100 | RSV-A NAb (neutralizing antibody) | 1 |
| | | | Respiratory Syncytial Virus PreF3 Ab.IgG (concentration) | 3 |
| | | | RSV-B NAb (neutralizing antibody) | 2 |
| V4-NB (Day 181) | post birth 3 | up to 100 | RSV-A NAb (neutralizing antibody) | 1 |
| | | | Respiratory Syncytial Virus PreF3 Ab.IgG (concentration) | 3 |
| | | | RSV-B NAb (neutralizing antibody) | 2 |

V = Visit; RSV-A/B: respiratory syncytial virus subtype A/B; **NA:** Not applicable; **NB:** Newborn. **IgG:** immunoglobulin G;

* Refer to [Table 11](#) and [Table 12](#)

CONFIDENTIAL209544 (RSV MAT-004)
Protocol Amendment 3 Final**Table 16 Molecular biology tests**

| Nasal swab sampling timepoint | | No. subjects | Component*** |
|-------------------------------|--------------------|---------------|-----------------------------------|
| Type of contact (timepoint) | Sampling timepoint | | |
| Maternal MA-RTI * | Event driven | Event-driven* | Respiratory Syncytial Virus A RNA |
| | | | Respiratory Syncytial Virus B RNA |
| Infant RTI** | Event driven | Event-driven* | Respiratory Syncytial Virus A RNA |
| | | | Respiratory Syncytial Virus B RNA |

*Includes maternal RTI hospitalizations

**Includes infant RTI hospitalizations

***Quantitative reverse transcription PCR will be performed on all specimens collected to evaluate RTI as specified in Section 8.4.5. To evaluate tertiary objectives, an Allplex Respiratory Viruses Panel or alternative may be performed for RSV A/B-positive samples, and (if deemed necessary) for RSV A/B-negative samples

8.1.4. Clinical safety laboratory assessments

Refer to Section 10.2 for the list of clinical laboratory tests for safety assessments required by the protocol. These tests must be conducted according to the clinical laboratory manual and the SoA (Section 1.3).

8.1.5. Immunological correlates of protection

No generally accepted immunological correlate of protection has been demonstrated so far for the antigen(s) used in the RSV maternal (RSVPreF3) vaccine.

8.2. Safety Assessments

The investigator and any designees are responsible for detecting, documenting, and reporting events that meet the definition of an AE, SAE, or AESI. The investigator and any designees remain responsible for following up AEs that are serious, considered related to the study intervention or participation in the study, are AESIs, or that caused the subject to discontinue the study.

Surveillance for / evaluation of respiratory tract illness is described in Section 8.4.

Electronic diary use is also described in Section 8.4.

8.2.1. Procedures for maternal subjects**8.2.1.1. Pre-vaccination procedures****8.2.1.1.1. Demographic data and lifestyle characteristics**

Demographic data may include (but are not limited to) geographic ancestry (race)*, ethnicity*, month of birth (if allowed per local regulation) and year of birth.

Lifestyle characteristics may include (but are not limited to) highest level of education, smoking status/exposures, household environment, and other factors that could place them at risk of adverse study outcomes.

CONFIDENTIAL209544 (RSV MAT-004)
Protocol Amendment 3 Final

*Differences in the safety and efficacy of certain medical products, including vaccines [Haralambieva, 2013; Pérez-Losada, 2009; Kollmann, 2013] have been observed in racially and ethnically distinct subgroups. These differences may be attributable to intrinsic factors (e.g., genetics, metabolism, elimination), extrinsic factors (e.g., diet, environmental exposure, sociocultural issues), or interactions between these factors. Therefore, both geographic ancestry (race) and ethnicity will be collected for all subjects participating in this study.

8.2.1.1.2. Medical/vaccination history

Obtain the maternal subject's medical/vaccination history by interviewing her and/or reviewing her medical records. Record any pre-existing maternal subject conditions, signs and/or symptoms present before the study vaccination in the eCRF.

- Record outcome of Level 2 ultrasound (also known as a fetal anomaly ultrasound scan or fetal morphology assessment). Please see the [Glossary of terms](#) for a description. If results are not available at screening, then the ultrasound can be performed as a study procedure under certain conditions. Refer to the SPM for further details. If abnormal, subjects will be referred per local standard of care.
- Information from additional antenatal / medical evaluations (external to study visits/procedures) may be collected before, during, or after a scheduled study visit but should only be recorded in the additional antenatal/medical evaluations eCRF.
- Record number of past pregnancies, their outcome(s) and any pregnancy-related complications.
- For the current pregnancy, record:
 - the subject's pre-pregnancy weight (i.e., weight during the months before the subject became pregnant). This information can be obtained either via medical record review or subject interview.
 - gestational age, along with GAIA level of certainty as defined in Section [10.7](#)
 - expected date of delivery (EDD) and method of estimation
 - number of prenatal visits attended up to the date of the study Screening visit,
 - approximate date of first prenatal visit,
 - results of any clinically significant, abnormal pregnancy screening laboratory tests,
 - any pregnancy-related complications
 - results of any procedures intended to screen for congenital anomalies.

CONFIDENTIAL209544 (RSV MAT-004)
Protocol Amendment 3 Final**8.2.1.2. Procedures carried out pre- and post-vaccination****8.2.1.2.1. Physical examination (General and obstetric examination)****Screening and Visits 1 through 6**

General examination should include:

- Height (only at screening)
- Weight, temperature, and systolic/diastolic blood pressure, heart rate and respiratory rate after at least 10 minutes of rest (at screening and at Visits 1 through 6). At Visit 1, temperature need only be measured once, pre-vaccination.
- Pulmonary examination including measurement of blood oxygen saturation (by pulse oximetry) and chest auscultation (at screening and at Visits 1 through 6).

Obstetric examination should include:

- Fetal heart tones, fetal movement and fundal height (at screening and visits 1-5)
- Presence of edema (at screening and visits 1 – 5)
- Symptom directed vaginal examinations (speculum and and/or manual). If performed, results (normal/abnormal: specify) will be recorded.

Visits 7 and 8, and all unscheduled visits

General and obstetric examination should be symptom-directed.

Any unscheduled visit for a medically attended respiratory tract illness **must** include the maternal subject assessments listed in Section [8.4.5](#).

